14.1 Schedule of Assessments

Evaluation	Screening ¹	Treatment	Post-Treatment							
		Day 1	Day 2	Day 3	Day 5	Day 8	Day 15 (±2 days)	Day 29 (±5 days)	Day 57 (±5 days)	Day 110 / EOS visit ²² (±5 days)
Informed Consent	X									
Demographic, medical history, and height	X									
Inclusion/exclusion criteria	X									
Physical examination and weight	X									X
Hepatitis B/C and HIV tests (local)	X ²									
Urine pregnancy test (local) ³	X ⁴									X
Clinical laboratory analyses ⁵ (local)	X ⁶			X		X				
Vital Signs (blood pressure, heart rate, respiratory rate) ⁷	X	X	X	X	X	X				X
12-Lead ECG ⁸	X					X				X
Chest x-ray ⁹	X			(X) ¹⁰						
Randomization		X								
Infusion of CT-P27 or placebo ¹¹		X								
Blood sampling for PK (only Subgroup [PK] Cohort) ¹²		X	X	X		X	X	X	X	X
Blood sampling for immunogenicity		X ¹³								X
Blood sampling for HI antibody (only Subgroup [PK] Cohort)		X ¹³						X		
Monitoring for immediate hypersensitivity ¹⁴		X								
Collection of a nasopharyngeal swab ¹⁵	X		X	X	X	X				
• Rapid influenza diagnostic test ¹⁶	x									
• Virus titer (qPCR and Cell culture)	x		x	x	x	x				

CONFIDENTIAL

34/62 page

Effective Date: 01-Aug-2018

Statistical Analysis Plan

Evaluation	Screening ¹	Treatment	Post-Treatment								
		Day 1	Day 2	Day 3	Day 5	Day 8	Day 15 (±2 days)	Day 29 (±5 days)	Day 57 (±5 days)	Day 110 / EOS visit ²² (±5 days)	

 The characterization of isolated influenza viruses 	x		(x)								
Physician assessment ¹⁷	X		X	X	X	X				X	
Flu-iiQ™ ¹⁸	X	X									
Body Temperature ¹⁹	X	X	X	X	X	X				X	
Concomitant medication ²⁰	X	X (continuously throughout the study)									
Adverse events ²¹	X	X (continuously throughout the study)									

ADE=antibody-dependent enhancement; AE=adverse event; ECG=electrocardiogram; eCRF=electronic case report form; EOS=End of Study; Flu-iiQ™=Influenza Intensity and Impact Questionnaire; HI=hemagglutination inhibition; HIV=Human immunodeficiency virus; PK=pharmacokinetic

Note: The assessments designated with an (X) will only be performed in selected subjects under the conditions explained in the footnotes.

1. For most subjects, obtainment of the informed consent form (ICF), screening for eligibility, randomization and treatment will occur on the same day. Though obtainment of the ICF may occur on the day prior to screening, randomization or treatment, it must be within 24 hours before the administration of study drug.
2. Hepatitis B surface antigen, Hepatitis B surface antibody, Hepatitis C virus antibody, and HIV will be assessed at screening in all subjects (mandatory). The results of these tests are not intended as eligibility assessments, but collected to provide baseline information.
3. For females of child-bearing potential only.
4. Urine pregnancy test will be performed at screening. If the urine pregnancy test gives equivocal results, a serum pregnancy test will be performed prior to study drug administration. Subjects with a positive test result will be excluded from the study.
5. Clinical laboratory analysis will be performed at screening and on Day 3, Day 8. All clinical laboratory analysis will be performed at the local laboratory. The laboratory tests to be performed are presented in Table 3 of CT-P27 2.2 protocol v5.0.
6. Clinical laboratory results will not be used for assessment of eligibility, but to establish baseline values.
7. Vital sign will be performed at screening, Day 1 (prior to infusion), Day 2 (±4 hours), Day 3 (±4 hours), Day 5 (±4 hours), Day 8 (±4 hours) and Day 110 (±5 days) after the start of the study drug infusion. Blood pressure (sitting) and heart rate will be measured after the subject has rested (sitting quietly) for at least 5 minutes.
8. 12-Lead ECGs will be performed at screening, on Day 8 (±4 hours), and Day 110 (±5 days) (or EOS visit in early termination case).

CONFIDENTIAL

35/62 page

Effective Date: 01-Aug-2018

Statistical Analysis Plan

9. Chest x-rays to evaluate the lower respiratory tract will be performed at screening and if the Investigator considers it is clinically appropriate, chest x-rays to evaluate the lower respiratory tract will be performed during the study.
 10. If symptoms have not relieved up to Day 3, chest x-ray will be performed to determine presence of secondary complications of influenza A infection.
 11. Treatment with study drug must occur no more than 48 hours after the onset of symptoms. If the adjustments of visit schedule is required, additional 12 hours can be allowed (Maximum onset of illness: 60 hours).
 12. PK blood sampling at:
 - Day 1: pre-infusion (within 15 minutes prior to the beginning of study drug infusion), at the end of infusion (within 15 minutes after the end of study drug infusion), and 1 hour (± 15 minutes) after the end of the study drug infusion.
 - Day 2: 24 hours (± 4 hours) after the start of the study drug infusion.
 - Day 3: 48 hours (± 4 hours) after the start of the study drug infusion.
 - Day 8: 168 hours (± 4 hours) after the start of the study drug infusion.
 - Day 15 (± 2 days), Day 29 (± 5 days), Day 57 (± 5 days), and Day 110 (± 5 days)/EOS visit.
 13. Day 1: prior to the study drug infusion.
 14. On Day 1, vital signs (including blood pressure and heart rate, respiratory rate), body temperature and ECG will be assessed at the time points listed below, and the subject will be monitored continuously over the period for possible immediate hypersensitivity reactions.
 - Vital sign and body temperature
 - Pre-infusion (within 15 minutes prior to the beginning of the infusion).
 - 30 minutes (± 15 minutes) after the beginning of the infusion.
 - Within 15 minutes after the end of the infusion.
 - 2 hour (± 15 minutes) after the end of the infusion.
 - Vital sign, body temperature and ECG
 - 1 hour (vital sign, body temperature: ± 15 minutes, ECG: $-30/+60$ minutes) after the end of the infusion.
- Emergency drugs and equipment suitable for assistance during anaphylactic reactions will be available during infusion with study drug.
15. When collecting the nasopharyngeal swabs, nasopharyngeal swabbing will be performed by trained site personnel. A nasopharyngeal swab sample will be obtained from all subjects up to Day 8 on the following schedule:
 - Screening (Nasopharyngeal swab samples will be collected for two times to be used for rapid influenza diagnostic test and virology assessment.)
 - Day 2: 24 hours (± 4 hours) after the start of the study drug infusion.
 - Day 3: 48 hours (± 4 hours) after the start of the study drug infusion.
 - Day 5: 96 hours (± 4 hours) after the start of the study drug infusion.
 - Day 8: 168 hours (± 4 hours) after the start of the study drug infusion.

CONFIDENTIAL

36/62 page

Effective Date: 01-Aug-2018

Statistical Analysis Plan

16. Sponsor-supplied or agreed in advance rapid influenza diagnostic test material will be used. And if there is available test result confirmed as influenza A prior to obtaining written informed consent and that result was from the influenza diagnostic test which is agreed with Sponsor in advance, that test result can be allowed. At screening, testing must be performed within 24 hours before study drug administration. Subjects with a negative test result by rapid diagnostic test, who have onset of symptoms within 48 hours (window of +12 hours is allowed) before study drug administration, can be rescreened only once.
17. The Investigator or designee will perform a symptom-directed physical examination (which should include, at a minimum, the examination of ear, nose, throat, sinuses, and lungs) and assessment for potential complications of influenza.
18. The subject will record the results of the Flu-iiQ™ in the diary.
 - Flu-iiQ™ will be recorded once by the subject at the screening visit and will be recorded twice a day (at approximately 12-hour intervals) from Day 1 to Day 8 (in the morning [between 6 and 10 AM, approximately] and in the evening [between 6 and 10 PM, approximately]).
19. Body temperature which a subject experiences in prior to screening will be collected and body temperature taken with any type of thermometer will be acceptable. However, from the screening period, Sponsor-supplied thermometer will be used.
 - Temperature will be measured by subject; It will be recorded twice a day (at approximately 12-hour intervals) from Day 1 to Day 8 (in the morning [between 6 and 10 AM, approximately] and in the evening [between 6 and 10 PM, approximately]).
 - Temperature will be measured by site personnel at site: at screening, Day 1 (prior to infusion), Day 2 (±4 hours), Day 3 (±4 hours), Day 5 (±4 hours) and Day 8 (±4 hours).
 - These will be used for assessment of endpoint.
20. Use of all medications, from 30 days prior to randomization and up until Day 110/EOS visit, will be recorded in the subject's eCRF.
21. AEs will be collected from the date the informed consent form is signed until Day 110/EOS visit.
22. EOS visit will be done at Day 110. But if a subject is early terminated from the study, EOS visit will be done to assess safety parameters at any time.

CONFIDENTIAL

37/62 page

Effective Date: 01-Aug-2018

Statistical Analysis Plan

Schedule of Assessments (Unscheduled Visits Subjects with Suspicious ADE)

Evaluation	Suspicious ADE Assessment				
	Day of occurrence ¹	Day 2	Day 3	Day 5	Day 8 ⁵
Collection of a nasopharyngeal swab	X	X	X	X	X

 • Virus titer (qPCR and Cell culture)² 	x	x	x	x	x

 • The characterization of isolated influenza viruses 	x	(x)			
Flu-iiQ™ ³			X		
Body Temperature ⁴			X		

1. The day of suspicious ADE occurrence.
 - Symptoms have not resolved or have worsened up to Day 8 (168 hours) after the administration of study drug in the opinion of the Investigator.
 - The subject develops a secondary influenza-like illness after Day 8 (168 hours).
2. Nasopharyngeal swab will be collected once a day up to Day 8 on the following schedule:
 - Day of occurrence
 - Day 2: 24 hours (±4 hours)
 - Day 3: 48 hours (±4 hours)
 - Day 5: 96 hours (±4 hours)
 - Day 8: 168 hours (±4 hours)
3. Flu-iiQ™ and the body temperature in the diary twice a day up to Day 8 (168 hours) from Day 1 to Day 8 (in the morning [between 6 and 10 AM, approximately] and in the evening [between 6 and 10 PM, approximately]).
4. Body temperature will be assessed by Sponsor-supplied thermometer.
5. If symptoms have not resolved or have worsened up to Day 8 after the day of ADE occurrence, same procedure will repeat.

CONFIDENTIAL

Statistical Analysis Plan

14.2 CTCAE Grades

- Grade 1 Mild; asymptomatic or mild symptoms; clinical or diagnostic observations only; intervention not indicated.
- Grade 2 Moderate; minimal, local or noninvasive intervention indicated; limiting age-appropriate instrumental Activities of Daily Living (ADL¹)
- Grade 3 Severe or medically significant but not immediately life-threatening; hospitalization or prolongation of hospitalization indicated; disabling; limiting self-care ADL²
- Grade 4 Life-threatening consequences; urgent intervention indicated.
- Grade 5 Death related to AE.

Note: Activities of Daily Living (ADL)

1. Instrumental ADL refer to preparing meals, shopping for groceries or clothes, using the telephone, managing money, etc.
2. Self-care ADL refer to bathing, dressing and undressing, feeding self, using the toilet, taking medications, and not bedridden.

Statistical Analysis Plan

14.2.1 Laboratory Grades

CTCAE Term	Laboratory Parameter	Level	Grade 1	Grade 2	Grade 3	Grade 4
Anemia	Hemoglobin	Low	<LLN - 10.0 g/dL	<10.0 - 8.0 g/dL	<8.0 g/dL	-
Alanine aminotransferase increased	Alanine Aminotransferase (ALT)	High	>ULN - 3.0 x ULN	>3.0 - 5.0 x ULN	>5.0 - 20.0 x ULN	>20.0 x ULN
Alkaline phosphatase increased	Alkaline phosphatase	High	>ULN - 2.5 x ULN	>2.5 - 5.0 x ULN	>5.0 - 20.0 x ULN	>20.0 x ULN
Aspartate aminotransferase increased	Aspartate Aminotransferase (AST)	High	>ULN - 3.0 x ULN	>3.0 - 5.0 x ULN	>5.0 - 20.0 x ULN	>20.0 x ULN
Blood bilirubin increased	Total Bilirubin	High	>ULN - 1.5 x ULN	>1.5 - 3.0 x ULN	>3.0 - 10.0 x ULN	>10.0 x ULN
Cholesterol high	Cholesterol	High	>ULN - 7.75 mmol/L	>7.75 - 10.34 mmol/L	>10.34 - 12.92 mmol/L	>12.92 mmol/L
CPK increased	Creatine Phosphokinase (CPK)	High	>ULN - 2.5 x ULN	>2.5 x ULN - 5 x ULN	>5 x ULN - 10 x ULN	>10 x ULN
Creatinine increased	Creatinine	High	>1 - 1.5 x baseline; >ULN - 1.5 x ULN	>1.5 - 3.0 x baseline; >1.5 - 3.0 x ULN	>3.0 baseline; >3.0 - 6.0 x ULN	>6.0 x ULN

CONFIDENTIAL

40/62 page

Effective Date: 01-Aug-2018

Statistical Analysis Plan

CTCAE Term	Laboratory Parameter	Level	Grade 1	Grade 2	Grade 3	Grade 4
Hemoglobin increased	Hemoglobin	High	Increase in >0 - 2 gm/dL above ULN or above baseline if baseline is above ULN	Increase in >2 - 4 gm/dL above ULN or above baseline if baseline is above ULN	Increase in >4 gm/dL above ULN or above baseline if baseline is above ULN	-
Hyperglycemia	Glucose	High	Fasting glucose value >ULN - 8.9 mmol/L	Fasting glucose value >8.9 - 13.9 mmol/L	>13.9 - 27.8 mmol/L;	>27.8 mmol/L;
Hyperkalemia	Potassium	High	>ULN - 5.5 mmol/L	>5.5 - 6.0 mmol/L	>6.0 - 7.0 mmol/L	>7.0 mmol/L
Hypernatremia	Sodium	High	>ULN - 150 mmol/L	>150 - 155 mmol/L	>155 - 160 mmol/L;	>160 mmol/L
Hypertriglyceridemia	Triglyceride	High	1.71 mmol/L - 3.42 mmol/L	>3.42 mmol/L - 5.7 mmol/L	>5.7 mmol/L - 11.4 mmol/L	>11.4 mmol/L;
Hyperuricemia	Uric acid	High	>ULN - 10 mg/dL (0.59 mmol/L)	-	-	>0.59 mmol/L;
Hypoalbuminemia	Albumin	Low	<LLN - 30 g/L	<30 - 20 g/L	<20 g/L;	-
Hypoglycemia	Glucose	Low	<LLN - 3.0 mmol/L	<3.0 - 2.2 mmol/L	<2.2 - 1.7 mmol/L	<1.7 mmol/L
Hypokalemia	Potassium	Low	<LLN - 3.0 mmol/L	-	<3.0 - 2.5 mmol/L	<2.5 mmol/L
Hyponatremia	Sodium	Low	<LLN - 130 mmol/L	-	<130 - 120 mmol/L	<120 mmol/L

CONFIDENTIAL

Statistical Analysis Plan

CTCAE Term	Laboratory Parameter	Level	Grade 1	Grade 2	Grade 3	Grade 4
Leukocytosis	White blood cell (WBC)	High	-	-	>100,000/mm ³ ; (>100x10 ⁹ /L)	-
Lymphocyte count decreased	Lymphocyte	Low	<LLN - 800/mm ³ ; <LLN - 0.8 x 10 ⁹ /L	<800 - 500/mm ³ ; <0.8 - 0.5 x 10 ⁹ /L	<500 - 200/mm ³ ; <0.5 - 0.2 x 10 ⁹ /L	<200/mm ³ ; <0.2 x 10 ⁹ /L
Lymphocyte count increased	Lymphocyte	High	-	>4000/mm ³ - 20,000/mm ³ ; (>4 - 20x10 ⁹ /L)	>20,000/mm ³ ; (>20x10 ⁹ /L)	-
Neutrophil count decreased	Absolute Neutrophil Count (ANC)	Low	<LLN - 1.5 x 10 ⁹ /L	<1.5 - 1.0 x 10 ⁹ /L	<1.0 - 0.5 x 10 ⁹ /L	<0.5 x 10 ⁹ /L
Platelet count decreased	Platelet	Low	<LLN - 75.0 x 10 ⁹ /L	<75.0 - 50.0 x 10 ⁹ /L	<50.0 - 25.0 x 10 ⁹ /L	<25.0 x 10 ⁹ /L
Proteinuria	Protein	High	1+ proteinuria; urinary protein	Adults: 2+ proteinuria	-	-

CONFIDENTIAL

42/62 page

Effective Date: 01-Aug-2018

Statistical Analysis Plan

CTCAE Term	Laboratory Parameter	Level	Grade 1	Grade 2	Grade 3	Grade 4
White blood cell decreased	White blood cell (WBC)	Low	<LLN - 3.0×10^9 /L	<3.0 - 2.0×10^9 /L	<2.0 - 1.0×10^9 /L	< 1.0×10^9 /L

Note: LLN= Lower Limit of Normal, ULN= Upper Limit of Normal

[1] Hyperglycemia was graded according to CTCAE which includes fasting glucose value although blood sample was taken regardless of fasting state.

[2] If suggested unit for CTCAE grading is not applicable to SI unit, it was converted to SI unit and applied.

[3] In case of numeric value for grading is identical such as Hypokalemia and Hyperuricemia, CTCAE grade which include numeric value only was applied, because abnormal laboratory value with clinical input was reported as an adverse event and graded accordingly.

Statistical Analysis Plan

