12.2 Clinical Laboratory Analyses

Clinical laboratory (hematology, biochemistry, urinalysis) tests will be performed in local laboratories and results will be converted to standard units that are defined as in the sections 12.2.1, and 12.2.2.

Hematology, biochemistry and urinalysis parameters will be labeled with a CTCAE term and grading will be applied to post-baseline values for the parameters where possible according to CTCAE v 4.03. When CTCAE grade is upon clinical input only, the grading will not be applied, but grade require numeric and partial clinical input, grade will be assigned based on the numeric portion only. The CTCAE terms and grades for applicable parameters are listed in [Appendix 14.2.1](#). The CTCAE grades for this analysis will be Grade 1 (Mild), Grade 2 (Moderate), Grade 3 (Severe) and Grade 4 (Life-threatening). The CTCAE Grade 5 (Death) will not be applied in this analysis since death cannot be determined from a numeric laboratory result. If the post-baseline result for a subject does not satisfy any CTCAE grade, it will be classified as "No Grade". If a laboratory parameter value falls within the local normal range, the grade will be classified as "No grade" even if the value has the numeric grade according to CTCAE v 4.03.

If the laboratory parameter value falls in outside the normal range: 'low' or 'high', they will be flagged in each visit. All hematology, biochemistry and numeric urinalysis data will be listed with high and low flags to show if a value is outside the normal range.

The results for all hematology, biochemistry and categorical urinalysis parameters will be categorized into Normal, Abnormal/Not Clinically Significant (NCS) or Abnormal/Clinically Significant (CS) using the local laboratory normal ranges used by study site and provided by local laboratory prior to analysis.

The number and percentage of subjects with a result for each grade will be summarized by CTCAE term, CTCAE grade and actual treatment group. The summary includes only the most severe case during the overall visits.

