12.2.3 Urinalysis

Numeric urinalysis parameters (pH, specific gravity) will be summarized by descriptive statistics for all scheduled collection times (Baseline, Day 3, Day 8). Categorical urinalysis parameters (Ketones, Protein, Glucose, Bilirubin, Nitrite, Urobilinogen, Occult Blood, Color) will be summarized in the form of shift table. Results of normality (Normal, Abnormal/NCS, and Abnormal/CS) will be summarized for all scheduled collection times.

Numeric and categorical parameters will be listed in separate listings. Both test result will be listed for each subject by actual treatment group, visit and individual test results.

If microscopic examination of sediment performed, the results will be listed.

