14.3.1.6	Safety	Summary of Treatment-Emergent Adverse Events Leading to Study Discontinuation	Listing 14.3.2.3 TEAE Leading to Study Discontinuation
14.3.1.7	Safety	Summary of Treatment-Emergent Adverse Events due to Infusion Related/Anaphylactic Reactions	Listing 14.3.2.4 TEAE due to Infusion Related/Anaphylactic Reactions
14.3.1.8	Safety	Summary of Treatment-Emergent Adverse Events due to Infusion Related/Anaphylactic Reactions (Signs & Symptoms)	Listing 14.3.2.5 TEAE due to Infusion Related/Anaphylactic Reactions: Additional Information (Signs & Symptoms)
14.3.2.1	Safety	Summary of Treatment-Emergent Serious Adverse Events	Listing 14.3.2.1 Serious Adverse Events
14.3.4.1	Safety	Summary of CTCAE grading	Listing 16.2.8.1 Hematology, Listing 16.2.8.2 Biochemistry, Listing 16.2.8.4 Urinalysis - Categorical Parameters
14.3.4.2	Safety	Change from Baseline in Descriptive Statistics of Hematology	Listing 16.2.8.1 Hematology
14.3.4.3	Safety	Shift Table of Hematology Results	Listing 16.2.8.1 Hematology
14.3.4.4	Safety	Change from Baseline in Descriptive Statistics of Biochemistry	Listing 16.2.8.2 Biochemistry
14.3.4.5	Safety	Shift Table of Biochemistry Results	Listing 16.2.8.2 Biochemistry
14.3.4.6	Safety	Change from Baseline in Descriptive Statistics of Urinalysis	Listing 16.2.8.3 Urinalysis - Numeric Parameters
14.3.4.7	Safety	Shift Table of Urinalysis Results	Listing 16.2.8.4 Urinalysis - Categorical Parameters

CONFIDENTIAL

56/62 page

Effective Date: 01-Aug-2018

Statistical Analysis Plan

14.3.5.1	Safety	Change from Baseline in Descriptive Statistics of Vital Signs and Body Temperature	Listing 16.2.9.1 Vital Signs and Body Temperature
14.3.5.2	Safety	Summary of Immediate Hypersensitivity Monitoring Interpretation	Listing 16.2.9.2 Immediate Hypersensitivity - Vital Signs and Body Temperature, Listing 16.2.9.3 Immediate Hypersensitivity - Electrocardiograms
14.3.5.3	Safety	Summary of Clinically Notable Vital Signs and Body Temperature Results during Hypersensitivity Monitoring	Listing 16.2.9.2 Immediate Hypersensitivity - Vital Signs and Body Temperature
14.3.5.4	Safety	Shift Table of Electrocardiogram Findings	Listing 16.2.9.4 12-Lead Electrocardiograms
14.3.5.5	Safety	Shift Table of Physical Examination Findings	Listing 16.2.9.5 Physical Examination and Weight
14.3.5.6	Safety	Change from Baseline in Descriptive Statistics of Weight	Listing 16.2.9.5 Physical Examination and Weight

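### The proteinuria row in SAP 14.2.1 stops at a closed 2+ category, so any urine protein result above 2+ would be counted as No Grade in the CTCAE grading table (14.3.4.1)

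*SAP*

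**What the plan says.** SAP 12.2 (Clinical Laboratory Analyses) brings urinalysis into the toxicity grading: "Hematology, biochemistry and urinalysis parameters will be labeled with a CTCAE term and grading will be applied to post-baseline values". Three further rules in that section matter here.

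- Unmatched results: "If the post-baseline result for a subject does not satisfy any CTCAE grade, it will be classified as" No Grade.
- Normal results: "If a laboratory parameter value falls within the local normal range, the grade will be classified as" No grade, so both kinds of result carry one label.
- Reporting: "The summary includes only the most severe case during the overall visits".

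In SAP 14.2.1 (Laboratory Grades) the Proteinuria row reads "1+ proteinuria; urinary protein" under Grade 1 and "Adults: 2+ proteinuria" under Grade 2. Grades 3 and 4 are dashes.

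SAP 12.2.3 (Urinalysis) treats protein as a categorical parameter and gives it a shift table: "Results of normality (Normal, Abnormal/NCS, and Abnormal/CS) will be summarized for all scheduled collection times". In SAP 14.7, Table 14.3.4.1 (the summary of CTCAE grading) names "Listing 16.2.8.4 Urinalysis - Categorical Parameters" as its only urinalysis source.

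**The concern.** A grading scheme should never give a more abnormal result a lower grade than a less abnormal one. Here the top filled category is a single level, not a threshold, and the fallback rule catches whatever lies beyond it. A programmer who follows the text would place the heaviest proteinuria in the same cell as a negative result.

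Clinical laboratory analyses, urinalysis included, are a secondary safety endpoint (protocol 8.2.3, SAP 3.2). Table 14.3.4.1 is the planned summary that shows the degree of urine protein abnormality by treatment group. A reader of that table could not tell that a No Grade count might include such subjects.

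**Working it through.** The plan states no figure to reproduce, so the check consists of applying the written rules.

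**Inputs.** From SAP 14.2.1: 1+ is Grade 1, 2+ is Grade 2, and Grades 3 and 4 are empty. From SAP 12.2: a result that meets no grade is No Grade, and each subject is shown at the most severe case over all visits. From SAP 12.2.3: the post-baseline collection times are Day 3 and Day 8. Assumed: a scale of negative, trace, 1+, 2+, 3+, 4+. The documents do not give the reporting levels.

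**Step 1: single results.**

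| Result | Grade as written |
|---|---|
| Negative, trace | No Grade |
| 1+ | Grade 1 |
| 2+ | Grade 2 |
| 3+, 4+ | No Grade |

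The order rises to 2+ and then drops to the bottom.

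**Step 2: worst case per subject.** No Grade is taken to rank below Grade 1, as the label implies.

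| Day 3, Day 8 | As written | With Grade 2 read as 2+ or higher |
|---|---|---|
| 1+, 1+ | Grade 1 | Grade 1 |
| 3+, negative | No Grade | Grade 2 |
| 3+, 1+ | Grade 1 | Grade 2 |
| 3+, 4+ | No Grade | Grade 2 |
| 4+, 2+ | Grade 2 | Grade 2 |

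A subject at 3+ and 4+ is grouped with normal subjects, below a subject at 1+ on both days. A subject who also has a 1+ or 2+ result is shown at that lower level, not lost.

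**Step 3: does other text close the gap?** Footnote [3] to the 14.2.1 table covers rows in which two grades share the same numeric value, with hypokalemia and hyperuricemia as its examples. It does not reach proteinuria above 2+. No quantitative urine protein is available as a substitute, because the numeric urinalysis parameters in SAP 12.2.3 are pH and specific gravity.

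**Step 4: is this the table's general style?** The table has 25 rows. In the other 24 the highest filled grade is open-ended, even where the higher cells are dashes: anemia ends at below 8.0 g/dL, hypoalbuminemia at below 20 g/L, and lymphocyte count increased at above 20 x 10^9/L. Proteinuria alone ends in a closed category, which points to an oversight in this row.

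**The case against.** The strongest reply is that little is lost.

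- A result above 2+ still counts as Abnormal/NCS or Abnormal/CS in the urinalysis shift table (14.3.4.7) and appears by subject and visit in Listing 16.2.8.4.
- If it is clinically significant, which under protocol 6.2.1 includes a need for treatment or for further diagnostic evaluation, it is reported as an adverse event (protocol 6.2.4). It is then graded for intensity (SAP 12.1) and tabulated with the other TEAEs.

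This stands and limits the point to Table 14.3.4.1. It does not remove the point, because the shift table does not separate 1+ from a heavier result, and a result judged not clinically significant has its degree shown in no other summary table.

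A second reply is that no document lists a level above 2+ or gives the test method. This also stands: if no laboratory reports above 2+, nothing changes.

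Third, the Grade 1 cell breaks off in mid-phrase, so some text of this row may have been lost when the PDF was read. The dashes under Grades 3 and 4 are nevertheless explicit.

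Fourth, a programmer might read 2+ as a floor. The SAP does not say so, and its fallback rule directs otherwise.

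A reader might go further and infer that the plan hides severe proteinuria from the safety report, or that it favours CT-P27 by masking a renal effect. The documents do not support either. The other outputs still show these results, and the readable text names no renal risk for antibodies described as directed at an exogenous protein (protocol 2.4.1). Much of the background is redacted, so that silence is not evidence in either direction.

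**Conclusion.** The rule as written gives a wrong ordering: in Table 14.3.4.1 a urine protein result above 2+ is No Grade and ranks below 1+. The conclusion rests on a literal reading of SAP 12.2 with 14.2.1, and on the assumption that at least some local laboratories report levels above 2+.

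The number of subjects affected cannot be derived from the documents. They are those with a post-baseline result above 2+ and no 2+ result at the other visit. They would appear as Grade 1 if the other result is 1+, and as No Grade otherwise. The error is confined to one descriptive safety table and touches no efficacy analysis. Severity is minor.

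**What to change.** In SAP 14.2.1, change the Grade 2 entry for categorical urine protein to 2+ or higher, so that no result above 2+ falls to No Grade. Because SAP 12.2 commits to CTCAE v4.03, the sponsor should check the revised wording against that version, which the appendix table does not reproduce in full.

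Optionally, footnote the number of subjects above 2+ in Table 14.3.4.1 by treatment group, since Grade 2 alone would not distinguish them.

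No general rule for all rows is needed, because the other 24 rows are already open-ended. The cost is one table cell, a small programming change and, if wanted, one footnote. No new data are required.
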